#### 6.2.14.7. Hospitalizations and Transfusions

The frequency and percentage of patients with any hospitalizations experienced during the study treatment period or 30-day post discontinuation follow-up period will be summarized by treatment arm.

## 6.2.15. Subgroup Analyses

Subgroup analyses of OS will be performed for each of following potential prognostic subgroup variables:

- All baseline stratification factors, including the number of prior chemotherapy regimens (1 vs. 2), performance status (ECOG 0 vs. 1), gender (male vs. female), and *KRAS* mutation (G12C vs. all others).
- Age (<65 years vs.  $\geq$ 65 years). Additional age cutoffs may be explored.
- Smoking status (current vs. former vs. never).
- Region (North America vs. Europe vs. Asia vs. Other).
- Race (Caucasian vs. Asian vs. Other).
- Prior immunotherapy (with vs. without).

If a level of a factor consists of fewer than 5% of randomized patients, analysis within that level will be omitted.

Analyses will be done within subgroup and, separately, across subgroups with a test of interactions of subgroups with treatment performed. Estimated HRs and CIs for the within subgroup analyses will be presented as a forest plot along with p-values for tests of interactions between subgroup variables and treatment. Cox proportional model in analyzing each of the subgroup will contain a term for treatment, the subgroup covariate of interest and the treatment by subgroup interaction term. The stratification factors will not be included in the model unless stratification factor is the subgroup being analyzed.

Analyses conducted specifically for the Japan Pharmaceuticals and Medical Devices Agency (PMDA) will be described in a separate SAP.

Other subgroup analyses may be performed as deemed appropriate. If any safety analyses identify important imbalances between arms, subgroup analyses of these endpoints may be performed.

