### 9.2. Materials and Supplies

Abemaciclib will be supplied by Lilly as capsules for oral administration. Abemaciclib capsules should be stored according to the temperature range listed on the product label, and should not be opened, crushed, or chewed.

Erlotinib will be supplied where required as tablets for oral consumption. Erlotinib should be stored according to the temperature range listed on the product label.

All study drug provided by Lilly will be labeled according to local country regulatory requirements. All medication should be kept out of the reach of children and stored in the original packaging/container provided.

Patients who meet all criteria for enrollment will be randomly assigned to receive either abemaciclib or erlotinib. If possible, treatment should begin as soon as possible when study drug is available.

Randomization will be stratified by the following factors:

- number of prior chemotherapy regimens (1 versus 2)
  - For purposes of stratification, immunotherapy does not count as a chemotherapy regimen. However, immunotherapy may be considered a prior treatment for eligibility as described in Section 7.1 (for example, if a patient received platinum-based therapy followed by immunotherapy, the number of prior chemotherapies for stratification is one).
- performance status (0 versus 1)
- gender (male versus female)
- *KRAS* mutation (GLY12CYS [G12C] versus all others)

Assignment to treatment groups will be determined by a computer-generated random sequence using an interactive web response system.

The chosen stratification factors have been identified as variables with the foremost influence on the primary objective of OS. Randomization will be performed separately within each of the 16 strata (or cells) defined by all combinations of these 4 variables.

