# 12. Sample Size and Statistical Methods

### 12.1. Determination of Sample Size

The primary objective of this study is to compare abemaciclib versus erlotinib with respect to OS in patients with Stage IV NSCLC whose tumors have detectable *KRAS* mutations (specifically, in codons 12 and 13 of the *KRAS* oncogene) and who have progressed after prior platinum-based therapy and received 1 other prior therapy or are not eligible for further chemotherapy.

The study will enroll approximately 450 patients in 3:2 randomization (approximately 270 patients in the abemaciclib arm and 180 patients in the erlotinib arm). The final analysis will occur when approximately 304 OS events have been observed.

Assuming an OS HR of 0.72, this sample size yields approximately 80% statistical power to detect superiority of the abemaciclib arm over erlotinib arm with the use of a 2-sided log-rank test and a type I error of .05.

If the true median OS for the erlotinib arm is 6.5 months, then the HR of 0.72 amounts to an approximately 2.5-month improvement in median OS for the abemaciclib arm under an additional assumption of exponential survival distribution.

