## 6.2.13. Health Outcomes and Quality of Life Evaluations

Patient-reported outcomes are measured through paper versions of the following:

- MD Anderson Symptom Inventory- Lung Cancer (with 11 exploratory items for brain metastases (9) and potential toxicities (2))
- EuroQol 5-Dimension 5 Level (EQ-5D 5L)

Data from the MDASI-LC instrument will be scored as described by Mendoza and colleagues (Mendoza et al. 2011).

Descriptive statistics will be used to describe several subscales and individual items by treatment arm and cycle: symptom severity (13 core items plus lung-cancer items), core severity (13 core items only), interference (6 interference items), 6 individual brain symptom items: irritability (affective); understanding, speaking, concentrating (cognitive); seizures (focal neurologic); appearance (generalized/ disease status) as well as 3 individual items headache, diarrhea and rash.

For each instrument, the analysis will include all cycles for which instrument is planned to measure and at least 25% of patients in each arm have an assessment. If the above criteria are met, a mixed model will be applied to compare treatment arms for symptom severity, core severity, interference subscales, each of 6 individual brain symptom items (irritability, understanding, speaking, concentrating, seizures, and appearance) as well as 3 individual items: headache, diarrhea and rash. The model will include baseline score as a covariate and an unstructured covariance matrix will be utilized if it converges. If the model cannot converge with an unstructured covariance matrix, the covariance matrix will be determined based on the Akaike Information Criterion (AIC).

If a patient does not complete all items on the MDASI-LC, the mean score for a subscale will be calculated when at least 50% of the items for that subscale were answered).

Based on literature (Farrar et al. 2001), it is suggested that worsening of pain by 2 points may be clinically relevant. Time to worsening in pain (worsening by 2 or more points in MDASI pain item or in WHO ladder code based on Table JPBK.6.5 whichever occurs first) will be described using the method of Kaplan and Meier and will be compared between 2 arms by a log-rank test. Worsening-free pain rate at 3, 6, 9, and 12 months (if available) will be compared between treatment arms.

Code	Description
0	No analgesia
1	Aspirin (for pain, not cardiovascular prophylaxis), acetaminophen, nonsteroidal anti-inflammatory drugs

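### OS subgroup Cox models omit the randomization factors that stratify the overall HR, so subgroup HRs sit slightly closer to 1 and lose some power

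*SAP*

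**What the plan says.** SAP section 6.2.10.2 estimates the overall OS HR from a Cox model with treatment as the factor, stratified by number of prior chemotherapy regimens, ECOG PS, gender and *KRAS* mutation as recorded in the IWRS.

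SAP section 6.2.15 gives each OS subgroup model three terms: treatment, subgroup and their interaction. It then states: "The stratification factors will not be included in the model unless stratification factor is the subgroup being analyzed". So the age, smoking, region, race and prior-immunotherapy models carry none of the four factors. A model for one stratification factor carries that factor. Within-subgroup HRs go on a forest plot with interaction p-values, and SAP section 6.2.1 tests interactions at a 2-sided 0.1 level. No reason for the omission is given.

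The protocol's randomization text (section 9.2) says: "The chosen stratification factors have been identified as variables with the foremost influence on the primary objective of OS". Protocol section 8.2 gives better power as one reason for stratifying.

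**The concern.** Readers judge each subgroup row of a forest plot against the overall HR. Here the two are different quantities: the overall HR is conditional on four prognostic factors and the subgroup HRs are not. In a Cox model, omitting a prognostic covariate moves the treatment HR toward 1 even under perfect randomization. A subgroup can therefore look a little weaker than the whole trial for a technical reason. Power also falls because the estimated effect is smaller, and subgroup and interaction analyses are where power is scarcest. The rule also departs from the plan's own use of these factors for PFS, response rates and the futility HR.

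**Working it through.** **Inputs from the documents** (Protocol 12.1): "Assuming an OS HR of 0.72, this sample size yields approximately 80% statistical power"; "2-sided log-rank test and a type I error of .05"; "The final analysis will occur when approximately 304 OS events have been observed"; "The study will enroll approximately 450 patients in 3:2 randomization". The control median is 6.5 months with exponential survival.

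**Assumptions not in the documents:** all four factors share one prognostic HR (1.0, 1.2, 1.5 or 2.0); factor prevalences are 45–65%; accrual is uniform over 30 months; blocks of 5 are used within the 16 strata; the subgroup is a random 50% or 25% of patients with the same true conditional HR of 0.72.

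**1. The plan's own figure.** Events = (1.960 + 0.842)² / [0.6 × 0.4 × (ln 0.72)²] = 7.849 / (0.24 × 0.1079) = 303.1, so 304. Power with 304 events = Φ(√(304 × 0.24) × 0.3285 − 1.960) = Φ(0.846) = 80.1%. The stated 80% reproduces, and this point does not affect it.

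**2. Subgroup standard error.** A half-sized subgroup has about 152 deaths. SE of log HR ≈ 1/√(152 × 0.24) = 0.166. The 95% interval around 0.72 is exp(−0.3285 ± 1.96 × 0.166), about 0.52 to 1.00.

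**3. Simulation**, 1000 trials per row, 450 patients, 304 deaths; the subgroup columns are for a 50% subgroup:

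| Per-factor HR | Overall HR, stratified | Subgroup HR, unadjusted | Subgroup HR, adjusted | SE, unadjusted / adjusted | Power, unadjusted / adjusted |
|---|---|---|---|---|---|
| 1.0 | 0.718 | 0.721 | 0.717 | 0.166 / 0.168 | 51.4% / 51.1% |
| 1.2 | 0.717 | 0.727 | 0.718 | 0.166 / 0.168 | 47.3% / 50.6% |
| 1.5 | 0.723 | 0.739 | 0.716 | 0.165 / 0.168 | 43.9% / 49.9% |
| 2.0 | 0.720 | 0.757 | 0.708 | 0.165 / 0.168 | 39.2% / 53.8% |

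Monte Carlo error on a mean subgroup log HR is about 0.166/√1000 = 0.005, or about 0.004 on the HR.

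**4. Size of the shift** for per-factor HRs of 1.2, 1.5 and 2.0:
- Unadjusted minus adjusted: 0.009, 0.023, 0.049.
- Unadjusted minus the true 0.72: 0.007, 0.019, 0.037. On the log scale this is 0.010, 0.026 and 0.050, or about 0.06, 0.16 and 0.30 of one subgroup SE.
- Unadjusted subgroup minus stratified overall, which is the comparison a forest-plot reader makes: 0.010, 0.016, 0.037.

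**5. Power loss.** The table gives 3.3, 6.0 and 14.6 points. As a closed-form check, power = Φ(√(152 × 0.24) × |ln HR| − 1.960). This is 51.0% at 0.72, 48.6% at 0.727, 44.7% at 0.739 and 39.0% at 0.757, so attenuation alone costs 2.3, 6.3 and 11.9 points. Together the range is about 2 to 15.

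**6. Unequal strengths.** With assumed HRs of 1.8/1.3/1.3/1.1 (1200 trials), unadjusted against adjusted is 0.732 against 0.713, with power 47% against 52%. With 2.2/1.6/1.5/1.3 it is 0.746 against 0.715, with power 43% against 51%. A separate repeat gave 0.732 against 0.714 (about 47% against 53%) and 0.745 against 0.719 (about 43% against 47%).

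**7. Why not 16 strata.** SE of log HR, unadjusted / main effects / 16 strata: about 0.166 / 0.168 / 0.181 in a 50% subgroup and 0.237 / 0.245 / 0.281 in a 25% subgroup. Full stratification inside subgroups does lose precision. Main effects cost little.

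**The case against.** The strongest reply is that an unadjusted subgroup HR is a valid randomized comparison, prespecified and supportive, and that choosing a marginal over a conditional estimate is a preference. The shift is at most about a third of a subgroup SE and would be invisible on the plot. Part of the gap in the tables is also not attenuation: with per-factor HR 2.0, the adjusted estimate overshoots the true 0.72 by 0.012 of the 0.049. In a level at the 5% threshold (0.05 × 450 ≈ 23 patients, about 15 deaths), treatment plus four covariates leaves about 3 deaths per parameter. Falling back to an unadjusted model there would mix two kinds of HR on one plot.

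Most of this stands, and it limits the point to a minor one. It does not explain why the overall and subgroup rows should differ in kind, and the mixing problem is solved by also showing an unstratified overall HR. OS Sensitivity Analysis 1 does not supply that HR, because it specifies only a test.

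A reader might infer more, and the documents do not support it:
- **That precision is lost in the Cox subgroup models.** The unadjusted SE is slightly smaller, not larger. Power falls because the estimate is attenuated.
- **That secondary comparisons ignore the factors.** PFS uses the stratified OS methods (SAP 6.2.10.3), ORR and DCR use a CMH test adjusted for all factors, and the futility HR is from a stratified Cox model (SAP 6.2.16.2).
- **That the pain test is stated to be unstratified.** SAP 6.2.13 says only that time to worsening "will be compared between 2 arms by a log-rank test". Where the SAP means unstratified, as for duration of response, it says so.
- **That the PRO models exclude the factors.** The text says "The model will include baseline score as a covariate" and is otherwise silent. The claim of foremost influence is made for OS only.

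**Conclusion.** The point holds as a minor one. The omission is explicit, it makes the subgroup HRs a different estimand from the stratified overall HR, and the direction of the effect follows if the factors are prognostic, as the protocol asserts. The size depends entirely on assumed strengths. For per-factor HRs of about 1.2 to 2.2, unadjusted and adjusted subgroup HRs differ by about 0.01 to 0.05, and a half-sized subgroup loses about 2 to 15 points of power. At the weak end the shift is close to simulation error. Even at the strong end it is small against an SE of about 0.17. The loss for interaction tests was not sized. The primary OS test, its type I error and its 80% power are unaffected.

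**What to change.** In SAP 6.2.15, replace the exclusion with a rule that each subgroup and interaction Cox model includes the four IWRS factors as main-effect covariates, not as 16 strata, omitting the factor that defines the subgroup. State that a level whose model does not converge falls back to the unadjusted model and is marked as such. Show an unstratified overall HR beside the forest plot, next to the stratified one, so that those rows have a comparable reference.

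The cost is a few covariates already collected, slightly wider intervals (SE 0.168 against 0.166 in a half subgroup, 0.245 against 0.237 in a quarter), and possible non-convergence in levels of about 23 patients.

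As an optional minor addition, enter the same factors in the PRO mixed models. A linear model has no attenuation, so the gain is only in the SE. Omitting factors that explain a share R² of the variance left after baseline score inflates the SE by 1/√(1 − R²): 0.5%, 1.0%, 2.6% and 5.4% for assumed R² of 1%, 2%, 5% and 10%. It would also help to state whether the pain log-rank test is stratified.

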### 6.2.16. Interim Analyses and Data Monitoring

#### 6.2.16.1. Safety Interim Analyses

The data monitoring committee (DMC) is responsible for providing external oversight of patient safety in Study JPBK independently of the Lilly study team and Lilly GPS.

During the study, safety interim analyses will be performed approximately every 6 months. The safety interim analyses will be conducted to evaluate the overall safety profile of Abemaciclib. At the recommendation of the DMC, the frequency of safety interim analyses may be modified.

At each interim analysis, the DMC may recommend the trial continue without modifications, continue with specific modifications, or be stopped for safety concerns. There will be no prespecified rules for stopping the trial due to safety concerns. The DMC members will review unblinded safety data at each interim analysis. If a significant safety signal is identified, the DMC may recommend a protocol amendment, termination of enrollment, and/or termination of study treatment. The recommendations of the DMC will be communicated to the Lilly Senior Management Designee and, if necessary, an Internal Review Committee.

In the event that safety monitoring uncovers an issue that needs to be addressed by unblinding at the treatment group level, members of the DMC can conduct additional analyses of the safety data. Additionally, unblinding of a limited number of Lilly representatives external to the study team may be required for evaluation of selected SAEs for determination of regulatory reporting.

#### 6.2.16.2. Futility and Efficacy Interim Analyses

One interim efficacy analysis is planned based on PFS endpoint and is for futility only. This interim analysis will be conducted by the DMC. There is no plan for interim efficacy analysis based on the OS endpoint. The DMC may call for additional, unplanned, interim efficacy analyses. Details of the DMC communication plan can be found in the DMC charter. The analysis will occur after approximately100 PFS events have been observed. The DMC will be instructed to recommend stopping the study for futility if the observed hazard ratio for PFS (as calculated using a stratified Cox proportional hazards model) is greater than 0.95. Only the DMC is authorized to evaluate unblinded interim efficacy and safety analyses. Study sites will receive information about interim results ONLY if they need to know for the safety of their patients.

### 6.2.17. Protocol Violations

Protocol violations that can be derived from the data and are related to inclusion/exclusion criteria or treatment will be summarized. These violations will include those defined by:

- Inclusion/Exclusion Criteria
  - o Diagnosis
  - Prior treatments received
  - o Age

- Performance Status
- Inconsistency in stratification factors: number of prior chemotherapy regimens (1 vs. 2), performance status (ECOG 0 vs. 1) and gender (male vs. female) between values captured in IWRS vs eCRF.
- Inconsistency in stratification factor, *KRAS* mutation (G12C vs. all others) between values captured in the IWRS vs the central laboratory system.
- Treatment
  - Dose delays
  - Dose reductions

## 6.2.18. Annual Report Analyses

Annual report analyses, including Developmental Safety Update Report (DSUR) and Investigational Brochure (IB) analyses, are described in the Abemaciclib Program Safety Analysis Plan.

### 6.2.19. Clinical Trial Registry Analyses

Additional analyses will be performed for the purpose of fulfilling the Clinical Trial Registry (CTR) requirements.

Analyses provided for the CTR requirements include the following:

Summary of AEs, provided as a dataset which will be converted to an XML file. Both SAEs and 'Other' AEs will be summarized by: treatment group, MedDRA PT.

- An AE is considered 'Serious' whether or not it is a treatment emergent adverse event (TEAE).
- An AE is considered in the 'Other' category if it is both a TEAE and is not serious. For each SAE and 'Other' AE, for each term and treatment group, the following are provided:
  - the number of participants at risk of an event
  - the number of participants who experienced each event term
  - the number of events experienced.
- Consistent with www.ClinicalTrials.gov requirements, 'Other' AEs that occur in fewer than 5% of patients/subjects in every treatment group may not be included if a 5% threshold is chosen (5% is the minimum threshold).
- Adverse event (AE) reporting is consistent with other document disclosures for example, the clinical study report (CSR), manuscripts, and so forth.

In addition, a participant flow will be created that will describe how many enrolled patients completed the study, and for those who did not, the frequency of each reason for not completing. This analysis will be based on study discontinuation, not treatment discontinuation. A patient will be identified as having completed the study if the patient dies while on the study or the patient had discontinued study treatment and is in follow up at the time of the final OS analysis. Patients who withdraw consent before the final OS analysis or who are still on treatment at the time of the final OS analysis will be identified as not completing the study.

# 7. Unblinding Plan

Study JPBK is a randomized, open label study. Randomization will occur using an IWRS system. Assignment to treatment groups will be determined by a computer-generated random sequence. Each patient in this study will be aware of his or her own assigned treatment group. At each investigative site, all staff involved in treating and caring for study patients will have full knowledge of treatment assignments for the patients under their care.

In order to maintain the scientific integrity of this trial, access to study data will be strictly controlled prior to the interim and final analyses. For the accumulated group-level data, treatment assignment will not be included, and other parameters that can disclose treatment assignment will be scrambled. Therefore, the sponsor and all investigative sites will remain blinded to treatment group assignments for the summary statistics and reports until the database lock for the final analysis. Dummy treatment assignment will be used in the reporting database for Lilly trial-level safety review until the database lock for the final analysis of overall survival. Interim analyses will be carried out approximately every 6 months by an independent DMC (external to Lilly) to monitor safety and efficacy. The DMC is unblinded and only the Statistical Analysis Center (SAC), which is independent of the sponsor, will perform analyses on unblinded data. Until the primary analyses, only the SAC and the DMC will be unblinded to the summary statistics and reports.

For the interim PK analysis to occur prior to the interim/primary analyses, the list of individuals that will have access to unblinded data will be provided with the PK/pharmacodynamic analysis plan, and documentation concerning their access to the data will be retained.

# Appendix 1. Abemaciclib Consolidated AE Terms

Consolidated Preferred Term / Consolidated	MedDRA Preferred Terms from CTCAE Mapping
System Organ Class	
Abdominal pain / Gastrointestinal disorders	Abdominal pain, Abdominal pain lower, Abdominal
	pain upper, Gastrointestinal pain
Anaemia / Blood and lymphatic system disorders	Anaemia, Haematocrit decreased, Haemoglobin
	decreased, Red blood cell count decreased
Fatigue / General disorders and administration site	Asthenia, Fatigue
Haematuria / Renal and urinary disorders	Blood urine present Haematuria
Hypercalcaemia / Metabolism and nutrition disorders	Blood calcium increased Hypercalcaemia
Hypercholesterolaemia / Metabolism and nutrition	Blood cholesterol increased. Hypercholesterolaemia
disorders	Blood enoiesteror increased, rryperenoiesteroraenna
Hyperglycaemia / Metabolism and nutrition disorders	Blood glucose increased, Hyperglycaemia
Hyperkalaemia / Metabolism and nutrition disorders	Blood potassium increased, Hyperkalaemia
Hypermagnesaemia / Metabolism and nutrition	Blood magnesium increased, Hypermagnesaemia
disorders	
Hypernatraemia / Metabolism and nutrition disorders	Blood sodium increased, Hypernatraemia
Hyperphosphataemia / Metabolism and nutrition	Blood phosphorus increased, Hyperphosphataemia
disorders	
Hypertension / Vascular disorders	Blood pressure diastolic increased, Blood pressure
	Increased, Blood pressure systolic increased,
Here anticiply and a serie / Match aligns and matrition	Dis ed trickes and in anosed. Here articles and a series
disorders	Blood inglycerides increased, hyperinglyceridaemia
Hypoalbuminaemia / Metabolism and nutrition	Blood albumin decreased, Hypoalbuminaemia
disorders	/ 71
Hypocalcaemia / Metabolism and nutrition disorders	Blood calcium decreased, Hypocalcaemia, Calcium
	deficiency
Hypoglycaemia / Metabolism and nutrition disorders	Blood glucose decreased, Hypoglycaemia
Hypokalaemia / Metabolism and nutrition disorders	Blood potassium decreased, Hypokalaemia
Hypomagnesaemia / Metabolism and nutrition disorders	Blood magnesium decreased, Hypomagnesaemia
Hyponatraemia / Metabolism and nutrition disorders	Blood sodium decreased, Hyponatraemia
Hypophosphataemia / Metabolism and nutrition	Blood phosphorus decreased, Hypophosphataemia
disorders	
Hypotension / Vascular disorders	Blood pressure diastolic decreased, Blood pressure
	decreased, Blood pressure systolic decreased,
	Hypotension
Intestinal obstruction / Gastrointestinal disorders	Gastrointestinal obstruction, Intestinal obstruction,
	Large intestinal obstruction, Small intestinal
	obstruction
Leukocytosis / Blood and lymphatic system disorders	Leukocytosis, White blood cell count increased
Leukopenia / Blood and lymphatic system disorders	Leukopenia, White blood cell count decreased
Lymphopenia / Blood and lymphatic system disorders	Lymphopenia, Lymphocyte count decreased
Myocardial infarction / Cardiac disorders	Acute myocardial infarction, Myocardial infarction

Consolidated Preferred Term / Consolidated	MedDRA Preferred Terms from CTCAE Mapping
System Organ Class	
Neuropathy / Nervous system disorders	Acute polyneuropathy, Anaesthesia, Axonal
	neuropathy, Burning sensation, Dysaesthesia,
	Hypoaesthesia, Neuralgia, Neuritis, Neuropathy
	peripheral, Paraesthesia, Peripheral sensory
	neuropathy, Polyneuropathy, Sensory disturbance,
	Sensory loss, Skin burning sensation, Toxic neuropathy
Neutropenia / Blood and lymphatic system disorders	Neutropenia, Neutrophil count decreased
Rash / Skin and subcutaneous tissue disorders	Exfoliative rash, Mucocutaneous rash, Rash, Rash
	erythematous, Rash follicular, Rash generalized, Rash
	macular, Rash maculo-papular, Rash maculovesicular,
	Rash morbilliform, Rash papular, Rash
	papulosquamous, Rash pruritic, Rash pustular, Rash
	vesicular, Vulvovaginal rash
Thrombocytopenia / Blood and lymphatic system	Platelet count decreased, Thrombocytopenia
disorders	
Urticaria / Skin and subcutaneous tissue disorders	Urticaria, Urticaria papular

CCI

Approver: PPD Approval Date & Time: 02-Oct-2017 16:20:04 GMT Signature meaning: Approved Leo Document ID = d202fb58-0ef1-4ff3-8238-87744fcd32b1

Approver: PPD Approval Date & Time: 10-Jul-2018 09:10:11 GMT Signature meaning: Approved Leo Document ID = d202fb58-0ef1-4ff3-8238-87744fcd32b1

Approver: PPD Approval Date & Time: 11-Jul-2018 20:06:14 GMT Signature meaning: Approved Leo Document ID = 6a4bff96-aad0-4dde-abcb-d607cb1615b2

Approver: PPD Approval Date & Time: 23-Aug-2018 14:44:33 GMT Signature meaning: Approved
